8. SAFETY EVALUATION

All subjects who enter the study will be assessed for safety. Safety will be monitored by AEs assessed at each post-dose visit, physical examination, vital signs, electrocardiogram and clinical laboratory tests. In addition, the Columbia Suicide Severity Rating Scale (C-SSRS) will be administered at Screening, Baseline and all subsequent scheduled visits to assess emergent suicidal thoughts or behaviors.

8.1 Overview of Safety Analysis Issues

Missing end dates for AEs will not be imputed. If end date information is not available, it will be assumed that the finding or event is ongoing.

Missing AE start dates will be imputed based on the following rules:

- If only the year is known, the date will be set to 01 January of that year. If the year is the same as the year of the first dose of study medication, the date will be set to the date of the first dose of study medication.
- If the year and month are known the date will be set to first day of the month. If the year and month are the same as the year and month of the first dose of study medication, the date will be set to the date of the first dose of study medication.
- If the start date is completely missing it will be set to the date of the first dose of study medication.

8.2 Overview of Safety Analysis Methods

All safety data will be analyzed descriptively using the Safety population described in Section 4.1.1.

8.3 Extent of Exposure

The length of exposure (in days) of study medication will be calculated based on the dates of first and last dosing of study medication (last dosing date - first dosing date + 1), by treatment and overall. Length of exposure will be summarized by treatment group on the Safety population as continuous values and for the following categories (which correspond to scheduled study visit timing): 1-7 days, 8-14 days, 15-21 days, 22-28 days, and >=29 days.

8.4 Adverse Events

All AEs will be coded using MedDRA Version 21.0.

An AE is considered treatment-emergent, if it started on or after the first dose of study medication is administered. If a subject terminates early from the study and has an AE after his/her last dosing date, the AE will be deemed as treatment-emergent if it occurs \leq 24 hours after the last dose and not as treatment-emergent if it occurs $>$ 24 hours after the last dose of study medication. AEs with partial start dates will be imputed as outlined in Section 8.1.

Summary Tabulations

An overview of the frequency, i.e., the number and percentage of subjects with at least one of the following AEs will be presented by treatment group:

- Treatment-emergent adverse events (TEAEs).

- TEAEs related to study medication.
- Severe TEAEs.
- Serious treatment emergent AEs (SAEs).
- SAEs related to study medication.
- AEs leading to death.
- AEs leading to premature withdrawal of study medication.

System Organ Class/Preferred Term Tabulations

The frequency of subjects reporting TEAEs will be summarized within each system organ class (SOC), preferred term (PT), and treatment group. The SOC terms and PTs will be presented in decreasing order of the total number of subjects (frequency) who experienced each adverse event. System organ class terms and PTs with the same frequency will be presented alphabetically.

If a single subject experiences the same AE more than once, the subject will be counted once per SOC and PT for that AE, using the most severe intensity or highest relationship to study medication.

The frequency of subjects reporting the following TEAEs will be presented:

- All TEAEs.
- All TEAEs by intensity.
- All TEAEs by relationship to study drug.
- All treatment-emergent SAEs.
- All TEAEs leading to premature discontinuation from study.

By-Subject Listings

By-subject listings including relevant information (i.e. treatment, age, sex, race, duration of AE, severity, relationship, outcome, action taken, etc.) will be presented for:

- All AEs.

- SAEs.
- AEs leading to death.
- AEs leading to premature discontinuation of study medication.

The onset of AEs will be calculated relative to the first dose of study medication. The duration of AEs in days will be calculated as the difference between the onset and resolution dates of the AE. If the AE is ongoing at the end of the study, or the resolution date is unknown, the duration will be presented as 'Unknown'.

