### **5.9.2 Concomitant Therapy**

Information on concomitant medications will be collected at each study visit through the Post Withdrawal Follow-Up Phone Call (Visit 8) or early termination.

Intermittent use of acetaminophen or non-steroidal anti-inflammatory medications is allowed. Use of non-sedating antihistamines, including Zyrtec, Claritin, and Allegra, as well as Nasonex will also be allowed during the trial. Acetaminophen is permitted for control of fever or pain, if needed. Short courses of prescription and non-prescription medications for treatment of acute illnesses such as the common cold, viral illnesses, and ear infections are permitted, provided they do not contain the medications listed in [Appendix B](#) of the protocol.

If a subject discontinues from the study early, study drug is to be discontinued for at least 24 hours prior to his/her beginning new ADHD therapy.

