**Blood and urine samples MUST be drawn after efficacy and safety assessments are completed.**

#### **6.1.5 Early Termination**

Every effort should be made to have subjects who withdraw early from the trial return to the site to complete an Early Termination Visit and return any unused study drug.

The following activities should be performed:

- Blood pressure and pulse (in triplicate via automated machine)
- Body weight
- Physical examination
- Resting 12-lead ECG
- Laboratory tests
  - Serum chemistry panel
  - Hematology
  - Urinalysis
  - Urine pregnancy test for females of child-bearing potential
- AISRS
- BRIEF-A
- DERS
- ASQ
- CGI-S
- CGI-I
- Follow-up C-SSRS
- AE assessment
- Concomitant medications assessment
- eCRF entry for early withdrawal
- Study drug accountability

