### **6.1.7 Post-Withdrawal Follow-Up Telephone Call – Visit 8**

**The following activities will be performed during a follow-up telephone call, 7 + 2 days after Visit 7, for subjects who complete the study:**

- AE assessment
- Concomitant medications assessment

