### **7.3 Collection of Adverse Events**

The collection of AE information will start with the first dose of study drug (Day 2) and continue through the post-withdrawal follow-up phone call (i.e., 7 days after Visit 7). The collection of SAE information will start with the first dose of study drug (Day 2) and continue 30 days after the subject's last dose of study drug. For subjects who terminate early, all AEs and SAEs should be treated as medically appropriate. Should a subject have an ongoing SAE at the last study contact or has an SAE within 30 days after Visit 7, the subject will continue to be followed as specified in Section 7.8.

To detect the occurrence of AEs and SAEs, the physician should use non-direct neutral questioning of the subject at each post-dose clinical visit. Information of AEs and SAEs may also be given voluntarily by the subject at any time during the study.

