### **9.8.1 Adverse Events**

Adverse events will be coded using the Medical Dictionary for Regulatory Activities (MedDRA) coding dictionary. Treatment-emergent AEs will be defined as any event with a start date occurring on or after first dose of study medication.

The incidence of treatment-emergent AEs will be summarized by body system, preferred term, and treatment group. If a subject reports the same AE more than once, then that subject will be counted only once for the summary of that AE, using the most severe intensity or highest relationship to study medication.

Treatment-emergent AEs will be summarized as follows:

- All treatment-emergent AEs;
- All treatment-emergent AEs by intensity;
- All treatment-emergent AEs by relationship to study drug;
- All treatment-emergent SAEs; and
- All treatment-emergent AEs that led to premature discontinuation from study.

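### SAP 8.4 ends treatment-emergent counting 24 hours after last dose for early terminators but sets no end for completers

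*SAP*

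**What the plan says.** SAP 8.4 starts with a rule for all subjects: an AE counts as treatment-emergent from first dose onward. It then adds an exception: "If a subject terminates early from the study and has an AE after his/her last dosing date, the AE will be deemed as treatment-emergent" provided that it starts no later than 24 hours after the last dose, and not when it starts more than "24 hours after the last dose of study medication". The SAP gives no end limit for a subject who completes.

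The supplied protocol, section 9.8.1, has only the start condition: "Treatment-emergent AEs will be defined as any event with a start date occurring on or after first dose of study medication". SAP 12.2 declares no analysis changes from protocol Version 3.0.

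Collection is set in protocol 7.3. AEs are collected to the follow-up call. For SAEs, "The collection of SAE information will start with the first dose of study drug (Day 2) and continue 30 days after the" last dose, with no exception for early terminators. Protocol 6.1.7 limits the Visit 8 call to completers: "The following activities will be performed during a follow-up telephone call, 7 + 2 days after Visit 7, for subjects who complete the study". For those who leave early, protocol 6.1.5 asks for one visit: "Every effort should be made to have subjects who withdraw early from the trial return to the site to complete an Early Termination Visit". No contact is scheduled after it.

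**The concern.** Whether a subject completes is decided after randomisation. Protocol 5.3 withdraws subjects who cannot tolerate their dose, so early termination can itself be an effect of treatment. SAP 8.4 makes the counting window depend on that outcome. If dropout differs between arms, the arms' TEAE and treatment-emergent SAE rows are not counted on the same basis, and a reader of the by-arm tables would not see this.

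Safety and tolerability is a secondary objective (protocol 2.2), and these descriptive tables are the main by-arm evidence on it. The primary efficacy analysis is not affected.

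**Working it through.** **1. The rules side by side**

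| | Completer | Early terminator |
|---|---|---|
| Treatment-emergent from (SAP 8.4) | first dose | first dose |
| Treatment-emergent until (SAP 8.4) | no end stated | 24 hours after last dose |
| Last scheduled AE contact (protocol 6.1.5, 6.1.7) | Visit 8 call, 7 to 9 days after Visit 7 | Early Termination visit |
| SAE collection ends (protocol 7.3) | 30 days after last dose | 30 days after last dose |
| SAE reported on day 10 off drug | treatment-emergent | not treatment-emergent |

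In the last row the event is reported in both cases and the collection window is the same. The different classification comes from the exception in SAP 8.4. In calendar time, 30 − 1 = 29 of the 30 SAE collection days fall outside the count for early terminators. That is a length of time, not a number of events.

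**2. How many subjects the rule could reach**

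Inputs are from protocol 9.1 and SAP 2.7: 87 per group for about 90% power, 104 randomised per arm, 312 in total, about 20% dropout.

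As a background check, n = 2 × (2.241 + 1.282)² × (13/7)² = 85.6, so 86 per group. Power at 87 is 0.905 (normal approximation) or 0.900 (t test). The stated 87 reproduces, and the point does not depend on it.

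- At the stated 20%: 0.20 × 104 = 20.8 per arm; 0.20 × 312 = 62.4, about 62 subjects.
- If 104 leaves the 87 used for power: 104 − 87 = 17 per arm (17/104 = 16.3%); 3 × 17 = 51 subjects.

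Both are upper limits. Anyone never dosed is outside the Safety Population (SAP 4.1.1), and subjects lost to follow-up are unlikely to yield later events.

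**3. What cannot be computed**

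The documents give no dropout by arm, no rate of events starting more than 24 hours after last dose, and no interval between last dose and the Early Termination visit. The change in any table row is therefore unknown. For scale only, one reclassified SAE moves an arm's row by 1/104 = 0.96 percentage points if all 104 are dosed.

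**4. Can the rule be applied as written?**

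Protocol 7.4.3 names the date of AE onset, and SAP 8.3 works from dosing dates. An event dated the day after last dose can fall on either side of 24 hours, so the boundary needs a convention that the SAP does not state.

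**5. The protocol comparison**

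Against the supplied 9.8.1, the exception is a change that SAP 12.2 does not declare. But the SAP rests on Version 3.0 (SAP 12.1 and 12.2), while the supplied protocol logs only Amendment #1. The SAP also has items that the supplied text lacks: THC in the drug screen (SAP 8.5 against protocol 6.4.6) and an HCV RNA row in the schedule (SAP 14.1 against Table 6.1.1). The wording of 9.8.1 in Version 3.0 is not available. The comparison in step 1 lies within SAP 8.4 and the collection rules, and the asymmetry in SAP 8.4 does not depend on the protocol version.

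**The case against.** The best defence is that the clause keeps out events caused by replacement treatment. Under protocol 5.9.2, after early discontinuation "study drug is to be discontinued for at least 24 hours prior to his/her beginning new ADHD therapy", whereas prohibited medications can be resumed only after Visit 8 (5.9.3, Appendix B). An AE several days after early termination may therefore belong to another drug. This is a fair reason to identify such events, but the SAP does not give it, and the clause applies whether or not new therapy was started. It also does not explain the SAE asymmetry after Visit 8: completers may then resume other medications too, and their SAEs still count.

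Three limits on the point stand:

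- **Ascertainment already differs.** Only completers get the Visit 8 call, so few late non-serious AEs may be collected from early terminators. Even for SAEs, no contact is scheduled after Visit 8 or after the Early Termination visit, so late reports depend on someone coming forward. A reader might infer that the whole difference between the groups comes from SAP 8.4. The documents support that only for how a reported event is classified.
- **Excluded events are not lost.** They remain in the by-subject listings. The overview rows for AEs leading to death and to withdrawal of study medication are not worded as treatment-emergent only. Events on drug that cause withdrawal still count.
- **No direction is shown.** A reader might infer that the rule flatters AR19, because intolerant subjects are withdrawn. Placebo subjects can also leave early, and no dropout by arm is given.

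A reader might also infer a proven, undeclared departure from the protocol. That needs Version 3.0 to match the supplied 9.8.1, which cannot be checked here.

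**Conclusion.** The asymmetry is explicit in SAP 8.4 and should be fixed. Early terminators and completers have different treatment-emergent windows, so the by-arm TEAE and treatment-emergent SAE tables depend on a post-randomisation outcome that can reflect tolerability. This finding needs no assumption about the protocol version.

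The rule could reach up to about 62 subjects at the stated 20% dropout, or 51 on the 104-to-87 reading. The effect on the tables is unknown in size and direction, and may be small or zero. The conflict with protocol 9.8.1 and SAP 12.2 is conditional on Version 3.0. This is a should-fix point on safety reporting and no threat to the primary result.

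**What to change.** 1. Delete the early-terminator exception in SAP 8.4, so that one definition (onset on or after first dose, through the collection window) applies to all subjects, SAEs included.
2. Flag events that start after recorded new ADHD therapy. The flag will be incomplete for late events: "Information on concomitant medications will be collected at each study visit through the Post Withdrawal Follow-Up Phone Call (Visit 8) or early termination".
3. Footnote the TEAE tables to say that collection of non-serious AEs after early termination is limited. Deleting the clause does not remove that difference.
4. If an on-treatment table is also wanted, apply one date-based cutoff, for example the day after last dose, to all subjects as a supplementary table. A cutoff in hours would need onset times that the protocol does not name.
5. Check 9.8.1 in Version 3.0. If the sponsor keeps a different rule, SAP 12.2 should declare it with a reason. That would settle the documentation question but not the unequal windows.

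The cost is one clause deleted, one flag and one footnote, with no new data. TEAE counts may rise slightly, and some added events may reflect replacement therapy, which is why the flag is needed.

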8.5 Clinical Laboratory Evaluations

The following laboratory tests will be performed:

- At Screening (Visit 1), End of Study (Visit 7) and at an Early Termination Visit (if necessary), laboratory tests will include a non-fasting serum chemistry panel, hematology (complete blood count), and urinalysis. Laboratory assessments are optional at Unscheduled Visits.
- CYP 2D6 genetic testing will be performed only at Baseline (Visit 2) for those randomized subjects who opt in. Subjects who opt out are still eligible for the study. During the trial, CYP 2D6 testing results will be blinded to the subject and investigative site in order to ensure protocol efficacy and safety assessments remain unbiased.
- At the Screening Visit (Visit 1), a serum pregnancy test will be performed for all female subjects of child-bearing potential. Urine dipstick pregnancy tests will be performed onsite at Visit 2 (Baseline) and Visits 4, 6, and 7 (End of Study) or early termination visit (if necessary) and may be performed at any time during study participation, if pregnancy is suspected. If positive, confirmation should be performed via a serum pregnancy test.
- A urine test for drugs of abuse will be performed at the site during Visit 1 (Screening) and Visit 2 (Baseline). The following drugs will be included: amphetamine, barbituates, benzodiazepines, cocaine, opiates, methadone, methamphetamine, tetrahydrocannabinol (THC)/cannabis, and phencyclidine (PCP).

All laboratory values will be presented in data listings indicating abnormal values for non-fasting serum chemistry, CBC, genetic testing, and tests for drugs of abuse; and positive values for pregnancy tests.

8.6 Physical Examinations

A full physical examination will be performed at Visits 1 (Screening), 7 (End of Study), and at an Early Termination Visit, if necessary. Although not scheduled, a full physical examination may be performed at any time (post-screening) for safety reasons. The following body areas and systems will be examined: head and neck, abdominal, chest, cardiovascular, heart, respiratory, musculoskeletal, skin, neurological and endocrine. Body weight will be measured at Screening (Visit 1), Baseline (Visit 2), and at the end of Study (Visit 7) or at the Early Termination Visit, if necessary.

Abnormal physical examination results performed prior to first dose of study drug will be summarized descriptively in the medical history table by treatment group. Abnormal results obtained on or after the first dose of study drug will be presented in the applicable adverse event table(s).

8.7 Vital Signs

Blood pressure and pulse will be assessed at all study visits and will be taken using automated machines programmed to take 3 consecutive readings (at least 2 minutes apart). Respiratory rate, height for BMI, and temperature will be measured at Screening (Visit 1) only.

Systolic blood pressure, diastolic blood pressure, pulse, respiratory rate, and temperature will be summarized descriptively for each visit, including change from Baseline (where applicable).

In addition, the incidence of sponsor defined potentially clinically significant (PCS) post-treatment vital sign values will be presented by treatment group and visit to examine the frequency and percentage of subjects that meet the PCS criteria outlined below:

- Heart Rate
 - ≥ 20 bpm increase
 - ≥ 20 bpm decrease
- Systolic Blood Pressure
 - ≥ 20 mmHg increase
 - ≥ 20 mmHg decrease
- Diastolic Blood Pressure

- ≥15 mmHg increase
- ≥15 mmHg decrease
- Weight
 - ≥5% increase
 - ≥5% decrease

8.8 Electrocardiogram

A 12-lead ECG will be recorded at Screening (Visit 1), End of Study (Visit 7) and at an Early Termination Visit (if necessary) by the Investigator or other designated, qualified individual from the study site. The ECGs will be read by a central reader(s). Although not scheduled, an ECG assessment may be performed at any time (post-screening) for safety reasons. Final assessment of normal, abnormal results and clinical significance of the ECG, including the central reader's report, will be made by the investigator.

Screening ECG measurements, overall interpretation, and individual diagnoses will be summarized descriptively on the Safety population. All ECG measurements (including safety-related post-screening values) will be presented in data listings.

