### 3.2.2 Safety Endpoints

All subjects who enter the study will be assessed for safety. Safety will be monitored by adverse events (AEs) assessed at each visit. In addition, the Columbia Suicide Severity Rating Scale (C-SSRS) will be administered at Baseline and all subsequent scheduled visits to assess emergent suicidal thoughts or behaviors. Medical history will capture all medical conditions at Visits 1 (Screening) and 2 (Baseline). Physical examinations and clinical laboratory tests will be conducted at Screening and at Visit 7 (End of Study) and also can be conducted at any subsequent visit as deemed necessary by the Principal Investigator. Safety will be assessed by the following measures throughout the study:

- Vital sign changes
- Changes in weight
- Incidence and severity of AEs
- Incidence of clinically significant changes from Baseline in the C-SSRS
- Electrocardiogram (ECG) changes
- Laboratory values

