## **9.8 Safety Analyses**

All safety data will be analyzed descriptively by treatment group using the Safety Population.

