### **9.8.2 Clinical Laboratory Assessments**

Hematology, blood chemistry, and urinalysis parameters will be summarized at Baseline and at Visit 7, as well as changes from Baseline to Visit 7. Laboratory values and changes from Baseline in laboratory values will be summarized descriptively overall and by treatment group.

A summary of shifts from Baseline to final evaluation will be provided for each treatment group for each parameter. The normal range for each parameter will be used to create categories of low, normal, or high. Any result higher than the ULN or lower than the LLN will be categorized as high or low respectively, and any result within the lower and upper limits of normal will be categorized as normal. The number and percentage of subjects in each treatment group in each shift category from Baseline to final evaluation will be shown for each parameter.

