### **9.8.3 Vital Signs and ECGs**

Vital sign measurements will be summarized at Baseline and at each study visit. In addition, changes from Baseline to each study visit in vital sign and ECG measurements will be summarized.

ECG measurements will be summarized at Baseline and at Visit 7. In addition, changes from Baseline to Visit 7 in vital sign and ECG measurements will be summarized.

The incidence of sponsor-defined, potentially clinically significant, post-treatment vital sign values will also be presented by treatment group.

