12.2 Changes in the Analysis Planned in the Protocol

This SAP is based on Version 3.0 of the AR19.004 clinical study protocol dated August 20, 2018. No changes in the analyses of the study are planned from this version of the protocol.

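### SAP 8.8 and 8.5 omit the post-dose ECG and laboratory change and shift tables that Protocol 9.8.2 and 9.8.3 plan, while SAP 12.2 declares no change

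*SAP*

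**What the plan says.** **Protocol.** Section 3.2.2 lists "Electrocardiogram (ECG) changes" and "Laboratory values" among the safety measures. Section 9.8 sets the general rule: "All safety data will be analyzed descriptively by treatment group using the Safety Population". Section 9.8.3 says "ECG measurements will be summarized at Baseline and at Visit 7", and adds changes from Baseline to Visit 7. Section 9.8.2 plans laboratory values at Baseline and Visit 7 and the changes between them, overall and by treatment group. It then says: "A summary of shifts from Baseline to final evaluation will be provided for each treatment group for each parameter".

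**SAP.** Section 8.8 states: "Screening ECG measurements, overall interpretation, and individual diagnoses will be summarized descriptively on the Safety population". Its next sentence sends all ECG measurements, including those after Screening, to listings. Section 8.5 gives one output for laboratory data: "All laboratory values will be presented in data listings indicating abnormal values for non-fasting serum chemistry" (the sentence goes on to blood count, genetic and drug-of-abuse results). Section 8.2 says in general terms that safety data are analysed descriptively. Section 12.2 declares: "No changes in the analyses of the study are planned from this version of the protocol".

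**Schedule.** In both documents the 12-lead ECG, serum chemistry, hematology and urinalysis are scheduled at Screening, Visit 7 and Early Termination. None is scheduled at Visit 2.

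**The concern.** An endpoint defined as a change cannot be addressed by a table of the pre-treatment value alone. The ECG has one scheduled post-dose time point, and that is the one SAP 8.8 leaves out of its summary. A programmer working from SAP 8.8 and 8.5 would build a Screening ECG table, an ECG listing and a laboratory listing, and could reasonably stop there.

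Safety and tolerability is a secondary objective. The protocol describes the drug as a sympathomimetic amine, notes that the l-isomer has the greater cardiovascular potency, and excludes subjects on QTcF and other ECG findings. Readers of the study report will expect to compare ECG intervals and laboratory shifts across 20 mg, 40 mg and placebo. If the tables are first specified after unblinding, the choices of reference value, visit and parameter will be made with the treatment codes known, and under SAP Section 10 the tables would be labelled exploratory.

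**Working it through.** No sample-size or alpha figure bears on this point. The check sets the two documents side by side and then counts what is affected.

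**1. ECG**
- Protocol 9.8.3: measurements at Baseline and Visit 7, and change to Visit 7. The by-arm presentation comes from the general rule in Protocol 9.8.
- SAP 8.8: summary at Screening; listing for everything. No Visit 7 or Early Termination summary, no change, and no stated split by arm.
- Result: no specified table contains a post-dose ECG measurement.

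**2. Laboratory**
- Protocol 9.8.2: values at Baseline and Visit 7, change, and shift categories from Baseline to final evaluation, by treatment group.
- SAP 8.5: listings with abnormal values marked. No summary, change or shift table is named.
- Result: a gap, but of a weaker kind. SAP 8.8 names a single time point for its summary, which points away from any other. SAP 8.5 is silent on summaries.

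**3. Does the SAP specify tables when it wants them?** Yes. SAP 8.7 sets out descriptive summaries by visit with change from Baseline for vital signs, and threshold counts by treatment group and visit. SAP 8.9 adds frequency summaries for the C-SSRS, where Protocol 9.8.4 planned only a listing. Against that pattern, the absence of tables from 8.5 and 8.8 is likely to be taken literally.

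**4. What is affected**
- Planned randomised subjects: 312, or 104 per arm (Protocol 9.1), each with at most one scheduled post-dose ECG and one post-dose laboratory set.
- At the planned dropout of about 20%: 312 × 0.20 = 62.4, so about 62 subjects would have that set at an Early Termination visit, if they attend one. The other 312 − 62.4 = 249.6, about 250, would have it at Visit 7.
- A table restricted to Visit 7 would therefore miss up to about 62 post-dose records. SAP Section 3 applies no visit windowing, so the table must name Early Termination explicitly.

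**5. Which record is the reference?** Protocol 9.8.2 and 9.8.3 refer to Baseline, but none of these tests is scheduled at Visit 2. By the schedule the reference can only be Screening, and neither document says so.

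**6. Note on stimulant washout**
- Screening runs from Day -30 to Day -1, and Visit 2 is Day 1. With no Day 0, seven days before Visit 2 is Day -7.
- Possible Screening days: 30. Days before the latest permitted stop, Day -30 to Day -8: 30 − 7 = 23.
- Protocol exclusion 19 allows current stimulant therapy at Screening. So a prior user's reference ECG may be recorded on a stimulant. The documents do not say how many subjects this concerns, and 23 of 30 counts days, not subjects.

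**The case against.** The strongest case on the other side is that the SAP is incomplete rather than in conflict with the protocol. SAP 8.2 covers all safety data, SAP 12.2 says nothing has changed, and SAP Section 3 already requires every data item to be listed, so the listing sentence in 8.5 need not exclude a summary. A reader might infer that Section 3's rule, under which specific sections prevail, makes 8.5 and 8.8 override 8.2 and so rule the tables out. The text does not support that: the rule concerns the general policies set out in Section 3, and 8.2 is not one of them. This part of the objection stands. It weakens the laboratory limb more than the ECG limb. It does not supply the missing specification, because 8.2 names no ECG or laboratory table and does not repeat the protocol's requirement to present results by treatment group.

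A reader might also infer that the trial would have no by-arm information on cardiac or laboratory safety at all. That goes too far. Abnormal findings reported as adverse events appear by treatment group under SAP 8.4, and SAP 8.7 covers pulse and blood pressure. Those outputs depend on investigator reporting or measure something else. They do not show ECG interval changes or laboratory shifts, but they are not nothing.

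The version caveat is fair. SAP 12.2 refers to protocol Version 3.0, and the supplied protocol cannot be confirmed as that version. There are small differences elsewhere: the SAP adds cannabis to the drug screen and an HCV RNA row to the schedule. So the omission cannot be called an undeclared change with certainty. Whatever Version 3.0 says, the SAP itself still specifies no post-dose ECG table.

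On washout, a reader might infer that an on-stimulant reference understates the ECG change on AR19. The documents support no such direction across ECG parameters. Screening may be split over several days, so the ECG can also follow an early stop. Randomisation leaves the between-arm comparison unaffected.

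**Conclusion.** The point holds as a gap between the SAP and the supplied protocol. SAP 8.8, followed literally, produces no table of post-dose ECG measurements. SAP 8.5 names no laboratory summary, change or shift table. Protocol 9.8.2 and 9.8.3 plan all of these, and SAP 12.2 reports no difference. The ECG limb is firm on the wording; the laboratory limb is an omission that a careful team might fill from the protocol.

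The extent is one scheduled post-dose ECG and one laboratory set per subject, at most 312 of each. The primary endpoint, the type I error and the efficacy analyses are not affected. The data are collected and listed, so nothing is lost beyond the planned analysis. It should be fixed before unblinding, but it does not threaten the trial's main conclusion.

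The conclusion assumes that the supplied protocol matches Version 3.0 in 9.8.2 and 9.8.3, and that the tables are programmed from the SAP text. Washout is a note only: it is a reason to read ECG change against placebo, not a separate defect.

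**What to change.** **SAP 8.8.** Replace the whole summary sentence with: *ECG measurements, overall interpretation and individual diagnoses will be summarised by treatment group at Screening and at Visit 7/ET, with change from Screening for measurements, on the Safety population.* Keep the listing sentence that follows.

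**SAP 8.5.** Add the Protocol 9.8.2 outputs by treatment group: actual values, change, and low/normal/high shifts to the final evaluation. Keep the listings.

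**Reference value.** State in both sections that Screening is the baseline for ECG and laboratory data.

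**SAP 12.2.** If the sponsor does intend to drop any of these tables, say so here and give the reason.

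**Interpretation.** Add one sentence saying that ECG change is to be read against placebo, since some Screening ECGs may have been taken on a stimulant. A split by stimulant use at the Screening ECG is optional. If it is made, SAP 5.2 anticipates partial and missing medication dates, so on/off status will sometimes rest on an imputed date.

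**Cost.** SAP wording and a few standard tables from data already collected. No new visit or procedure is needed.
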